6.5.2 Immune-Related Adverse Events

A high level of awareness for the possibility that an AE may be an immune-related AE (irAE) is necessary in the management of patients receiving pembrolizumab because the presentations of an irAE can be subtle, and other causes must be ruled out. An irAE can occur at any point during treatment with pembrolizumab. It is imperative to establish the correct diagnosis promptly, determining severity based on Common Terminology Criteria for Adverse Events (CTCAE) grading and initiating treatment with steroids, if necessary, and holding further pembrolizumab treatment is essential (49).

Immune checkpoint blockade therapies have been associated with several syndromes resulting from the breaking of immunological tolerance in normal tissues (34, 60, 72). These syndromes include but are not limited to: pneumonitis, colitis, autoimmune hepatitis, arthritis, glomerulonephritis, myocarditis and cardiomyopathy, hypophysitis, thyroiditis, or other autoimmune endocrinopathies. The occurrence of any of these syndromes dictates interruption and potentially discontinuation of study drug administration pending further evaluation and reporting them to the Sponsor as AESIs. Most low-grade immune-related AEs (irAEs) can be

managed symptomatically. Persistent low grade or moderate toxicities may require treatment with corticosteroids or in refractory cases other immune suppressing agents such as mycophenolate or infliximab. High-grade immune-related toxicities will, in almost all cases, require treatment with corticosteroids.

For the purposes of the safety management, no distinction should be made as to which drug is the causative agent and both agents stopped (temporarily held or discontinued).

Temporary interruptions of margetuximab and/or pembrolizumab may be required in the event of treatment-related immune-related toxicity. General guidelines for specific toxicity regarding dosing and treatment are provided below. All toxicities will be graded according to NCI CTCAE v4.03.

6.5.2.1 Diarrhea or Colitis

Diarrhea that develops in patients while receiving pembrolizumab may reflect immune reactivity against normal colonic epithelium and careful monitoring for potential immune related colitis should be instituted. Patients should be monitored closely for evidence of diarrhea or other change in bowel habits as well as other signs and symptoms suggestive of colitis. Patients who develop signs or symptoms including abdominal pain, bloating, nausea, vomiting, diarrhea or blood in the stools should be evaluated carefully for potential colitis.

- Grade 1 diarrhea
 - Closely monitor the diarrhea until resolution.
- Grade 2 diarrhea
 - Hold pembrolizumab and margetuximab
 - Increase frequency of monitoring until resolution
 - Symptomatic management
 - Loperamide/diphenoxylate
 - Consider low dose steroids, if clinically indicated.
 - Consider management as per Grade 3 diarrhea with prolonged Grade 2 event lasting more than 5 to 7 days or relapsed diarrhea.
- Grade 3 diarrhea
 - Hold pembrolizumab and margetuximab
 - Hospitalize patient promptly for further evaluation and management including:
 - Bowel rest
 - Supplemental IV fluids with close monitoring of fluid and electrolyte status.

- Monitoring of frequency of bowel movements
 - Consider imaging to rule out bowel obstruction or perforation
 - Consideration of colonoscopy as appropriate
 - Implementation of initial empiric immune suppression consisting of IV corticosteroids using methylprednisolone at a dosage of 2 mg/kg/day divided twice daily. As tolerated, patients may be converted to oral corticosteroids (i.e., prednisone 2 mg/kg/day divided twice daily) and tapered as appropriate guided by the patients' clinical status.
 - Taper corticosteroids as clinically indicated
 - For patients with severe colitis, or those who do not respond to corticosteroids, additional immune suppression with anti-TNF- α antibodies (i.e., infliximab) should be considered early in the course.
- Consider restarting pembrolizumab and margetuximab if:
 - It is determined there is no colitis and an alternative cause of diarrhea is found, and
 - Diarrhea resolves to \leq Grade 1 within 14 days
- Grade 4 diarrhea
 - Discontinue pembrolizumab and hold margetuximab
 - Treat as for Grade 3

6.5.2.2 Hepatic Toxicity

6.5.2.2.1 Elevations in Transaminases

Management guidelines for patients experiencing hepatic toxicity are as follows:

- Grade 1 elevations
 - No specific therapy required
- Grade 2 elevations
 - For elevations in transaminases 3 to 5 \times ULN (Grade 2), rule out viral and other etiologies, and consider immediate oral steroids such as prednisone 60 mg/day divided twice daily, and hold pembrolizumab and margetuximab.
 - If improvement to \leq Grade 1 does not occur within 48 hours with oral steroids, consider IV steroids such as methylprednisolone at 2 mg/kg/day divided twice daily or oral steroids such as prednisone 60 to 120 mg per day, divided twice daily

- Resume pembrolizumab and margetuximab at the next scheduled dose if:
 - No more than one dose of pembrolizumab and margetuximab was missed
- If improvement to \leq Grade 1 does not occur within 14 days, discontinue pembrolizumab and margetuximab.
- Grade 3 elevations
 - Discontinue pembrolizumab and margetuximab
 - Initiate IV steroids and,
 - If no response to corticosteroid therapy within 3 to 5 days is observed, consider adding immune suppression therapy with mycophenolate. Do not use infliximab in these cases because of a potential for autoimmune hepatitis (40).
 - Monitor liver function tests at least twice weekly (or more frequently as clinically appropriate in the judgment of the investigator) until transaminases have returned to Grade 1 or baseline.
- Grade 4 elevation
 - Discontinue pembrolizumab and margetuximab
 - Treat as for Grade 3 elevation.

6.5.2.2.2 Elevations in Total Bilirubin

Management guidelines for patients experiencing elevations in total bilirubin are as follows:

- Grade 1 elevations
 - No specific therapy required
- Grade 2 elevations
 - Hold pembrolizumab and margetuximab until improvement to \leq Grade 1.
 - Consider oral steroids
 - If improvement to \leq Grade 1 does not occur within 14 days, discontinue pembrolizumab and margetuximab and begin oral steroids.
- Grade 3 elevations
 - Discontinue pembrolizumab and margetuximab
 - For elevations in total bilirubin $> 5 \times$ ULN, permanently discontinue pembrolizumab and margetuximab and initiate IV steroids and,

- If no response to corticosteroid therapy within 3 to 5 days is observed, consider adding immune suppression therapy with mycophenolate. Do not use infliximab in these cases because of a potential for autoimmune hepatitis (40).
- Monitor liver function testing at least twice weekly (or more frequently as clinically appropriate in the judgment of the investigator) until transaminases have returned to Grade 1 or baseline.
- Grade 4 elevations
 - Discontinue pembrolizumab and margetuximab
 - Treat as for Grade 3 elevation

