- Any Grade 3 elevation of one or more transaminases $> 5.0 - 8.0 \times$ ULN that does not resolve to Grade 2 (i.e., $> 2.5 - 5.0 \times$ ULN) within 7 days and Grade 1 (i.e., $> ULN - 2.5 \times$ ULN) within 14 days. In addition, steroids must be tapered to ≤ 10 mg of prednisone or equivalent per day, by Day 14. Please see [Section 6.5.2.2](#) for further management guidelines.
- A Grade 3 elevation of total bilirubin that is $> 5 \times$ ULN, irrespective of duration.
- Any Grade 3 elevation of total bilirubin $> 3.0-5.0 \times$ ULN that does not resolve to Grade 2 (i.e., $> 1.5-3.0 \times$ ULN) within 7 days and Grade 1 (i.e., $> ULN-1.5 \times$ ULN) within 14 days. In addition, steroids must be tapered to ≤ 10 mg of prednisone or equivalent per day, by Day 14. Please see [Section 6.5.2.2](#) for further management guidelines.
- Any event meeting the criteria for Hy's law as follows (all three features):
 - Aspartate aminotransferase (AST) and/or alanine aminotransferase (ALT) $> 3 \times$ ULN.

- Concurrent elevation of total bilirubin $> 2 \times$ ULN without initial evidence of cholestasis (e.g., elevated serum alkaline phosphatase [ALK-P]).
- No alternative etiology can be identified.

Dose Escalation Rules

The **Dose Escalation Phase (Part A)** of this trial will proceed using a conventional 3 + 3 approach, and will begin with enrollment of 3 patients at a dose of 200 mg pembrolizumab administered as an IV infusion once every 3 weeks and an initial dose of 10 mg/kg margetuximab administered as an IV infusion once every 3 weeks. Successive dose escalation cohorts will be enrolled as outlined below. The MTD or MAD will be determined based on the assessment of DLTs during the DLT evaluation period. Patients who are not evaluable for safety for the full DLT evaluation period for reasons other than study drug-related toxicity will be replaced in the same dose-level cohort.

- If 0 of the first 3 patients treated at a given dose level experience a drug-related DLT during the DLT evaluation period, the dose will be escalated and 3 patients will be enrolled and treated at the next higher dose level.
- If 1 of the first 3 patients treated at a given margetuximab dose level experiences a drug-related DLT, then 3 additional patients will be enrolled at that dose level (thus making a total of 6 patients in this cohort) to further assess the safety of the combination.

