10. Measurable disease as per Response Evaluation Criteria in Solid Tumors (RECIST) 1.1 (**Appendix 7**) and documented by computed tomography (CT) and/or magnetic resonance imaging (MRI). Patients with evaluable disease only will not be enrolled on this study. Note: Lesions to be used as measurable disease for the purpose of response assessment must either a) not reside in a field that has been subjected to prior radiotherapy, or b) have demonstrated clear evidence of radiographic progression since the completion of prior radiotherapy and prior to study enrollment.
11. Patients should have a formalin-fixed, paraffin embedded tumor specimen or unstained slides identified and available for analysis, to enable determination of the expression of HER2 and PD-L1 within tumor specimens using IHC staining.

Laboratory Features:

12. Acceptable laboratory parameters as follows:
 - a. Platelet count $\geq 100 \times 10^3/\mu\text{L}$ without transfusion within 2 weeks prior to the initiation of study drug.
 - b. Absolute neutrophil count (ANC) $\geq 1.5 \times 10^3/\mu\text{L}$ in the absence of any growth factor support within 2 weeks prior to the initiation of study drug.
 - c. Hemoglobin (Hgb) ≥ 9 g/dL.
 - d. ALT/AST $\leq 3.0 \times \text{ULN}$; for patients with hepatic metastases, ALT and AST $\leq 5 \times \text{ULN}$.
 - e. Total bilirubin $\leq 1.5 \times \text{ULN}$, except patients with Gilbert's syndrome, who may enroll if the conjugated bilirubin is within normal limits.
 - f. Creatinine < 2 mg/dL, or a calculated or measured creatinine clearance > 50 mL/min.

Reproductive Features:

13. Female patients of childbearing potential (not surgically sterilized and between menarche and 1 year postmenopause) must have a negative urine pregnancy test performed within 72 hours prior to the initiation of study drug administration. Further, female patients of childbearing potential must agree to use highly effective contraceptive measures from the time of consent through 120 days after discontinuation of study drug administration.

For Canadian patients only: Female patients of childbearing potential must have a negative pregnancy test prior to every cycle of pembrolizumab.

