7.9.5 Reporting of Adverse Events to the Sponsor

Throughout the study, the investigator must document all AEs on the eCRF in a timely manner. Adverse events will be collected and followed from the time the patient provides informed consent for the study (see [Section 7.1](#)) until 28 days following the last dose of study drug or the End of Treatment Visit or until the start of a subsequent systemic anticancer therapy (whichever occurs first). After the completion of the 28 day-period or start of a subsequent systemic anticancer therapy, only treatment-related AEs will be reported. If a patient experiences an AE after the informed consent document is signed and prior to treatment with study drug, it should be captured as medical history; however, if the investigator believes the AE may have been caused by a protocol-related procedure it will be recorded as an AE and entered onto the eCRF.

To identify the occurrence of any new medical complaints or worsening of previous complaints, non-leading questioning should be posed to the patient.

Events related to disease progression/worsening of underlying disease (including those with a fatal outcome) will be collected as efficacy endpoints, and not documented as AEs/SAEs. These events may not qualify for expedited reporting to regulatory agencies if consistent with expected rates of progression for the underlying disease. However, if an AE/SAE occurs in a patient and it is unclear if the event is due to progressive disease, the AE/SAE should be reported.

Any serious adverse event, or follow up to a serious adverse event, including death due to any cause other than progression of the cancer that occurs to any patient from the time the consent is signed through 90 days following cessation of treatment, or 28 days following cessation of treatment if the patient initiates new anticancer therapy, whichever is earlier, whether or not related to the Sponsor's product, must be reported within 24 hours to the Sponsor.

After 28 days following the last dose of study drug administration, if an Investigator becomes aware of an SAE that s/he suspects is related to study drug, the Investigator should report the event to the Sponsor.

If a patient reports signs and symptoms that represent a single medical syndrome, diagnosis, or concept, the syndrome/diagnosis/concept should be documented (e.g., cough, runny nose, fever = Upper Respiratory Tract Infection) in the eCRF.

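### In the total-bilirubin guideline, the twice-weekly liver-test minimum for Grade 3-4 ends on transaminases, so it can lapse while bilirubin is still Grade 3-4

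*Protocol*

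**What the plan says.** Section 6.5.2.2.2 of the protocol covers elevations in total bilirubin, grade by grade.

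- **Grade 2:** the instruction is "Hold pembrolizumab and margetuximab until improvement to" Grade 1 or below. Both drugs are discontinued if that has not happened within 14 days.
- **Grade 3:** both drugs are discontinued. Above 5 x ULN the discontinuation is permanent and IV steroids are started, with mycophenolate considered if there is no response in 3 to 5 days. Liver function is then monitored by "testing at least twice weekly (or more frequently as clinically appropriate in the judgment of the investigator) until transaminases have returned to Grade 1". A return to baseline also satisfies the condition.
- **Grade 4:** both drugs are discontinued and the instruction is "Treat as for Grade 3 elevation", so the monitoring line carries over.

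The preceding section, 6.5.2.2.1, deals with transaminases and gives its Grade 3 monitoring line the same end-point: "until transaminases have returned to Grade 1 or baseline". The parent section, 6.5.2, sets the status of all this text: "General guidelines for specific toxicity regarding dosing and treatment are provided below". The SAP does not address the point.

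**The concern.** A monitoring rule in a section about bilirubin should end when bilirubin has recovered. This one ends when transaminases have recovered. The near-identical wording in the transaminase section, where it fits, suggests that the line was carried over and not adapted. Nothing in the protocol gives a reason to change analyte at Grade 3-4, and the Grade 2 rules in the same section do depend on bilirubin.

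What is at stake is safety follow-up after Grade 3-4 bilirubin has stopped both drugs. This line is the only one that says how often liver tests are repeated and until when. If it expires early, the interval and the end of bilirubin re-testing are left to the investigator's judgment and the general adverse-event rules.

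**Working it through.** The plan has no figure to reproduce. The check is to read the rules side by side and ask whether any of them sets a test interval that runs until bilirubin recovers.

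**1. Which analyte governs each rule**

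| Place | Event managed | Criterion is based on |
|---|---|---|
| 6.5.2.2.1, Grade 3-4 | Transaminases | Transaminases |
| 6.5.2.2.2, Grade 2 | Total bilirubin | Total bilirubin |
| 6.5.2.2.2, Grade 3-4 monitoring | Total bilirubin | Transaminases |
| Synopsis, hepatic DLT ("Any Grade 3 elevation of total bilirubin") | Total bilirubin | Total bilirubin |

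Only the third row switches analyte.

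**2. When the minimum ends**

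- *Bilirubin lags.* Transaminases reach Grade 1 or baseline first. The stop condition is met and the minimum ends with bilirubin still Grade 3-4.
- *Bilirubin rises alone.* Transaminases are already at Grade 1 or baseline, so on a literal reading the condition is met from the outset.

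**3. How far apart the analytes can be at that moment**

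The synopsis DLT text supplies these grade limits:

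- Grade 1 bilirubin ends at 1.5 x ULN.
- Grade 3 bilirubin starts above 3.0 x ULN.
- Grade 1 transaminases end at 2.5 x ULN. Section 6.5.2.2.1 describes Grade 2 as 3 to 5 x ULN, which would put the limit at 3 x ULN.

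Ratio of the Grade 3 threshold to the Grade 1 ceiling for bilirubin: 3.0 / 1.5 = 2.0.

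So the minimum can end with transaminases at or below 2.5 x ULN (3 x ULN on the other reading) while bilirubin is more than 2.0 times its Grade 1 ceiling. That ceiling is also the entry limit in Section 5.1, except in Gilbert's syndrome. Patients with hepatic metastases may enter with ALT and AST up to 5 x ULN, so for them the baseline alternative can be met at still higher transaminases.

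**4. Whether another rule fills the gap**

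- *Scheduled chemistry (Appendix 2).* The panel includes total and direct bilirubin, but it follows dosing cycles, which have stopped, and the End of Treatment Visit. Section 8.3 makes that visit optional. No chemistry is scheduled at follow-up visits.
- *AE reporting (7.9.5, 7.9.5.1).* Grade 3 and 4 laboratory findings are reported as AEs or SAEs. "Adverse events will be collected and followed from the time the patient provides informed consent for the study", but only up to 28 days after the last dose, the End of Treatment Visit or new anticancer therapy, whichever is first. No test interval is given.
- *End of Study (8.3).* Its timing takes account of ongoing AEs, again without an interval.
- *SAE follow-up (7.9.5).* This runs to resolution, but for SAEs only and without an interval.
- *24-hour reports (5.3, 7.9.2.6).* These are notifications, not monitoring.
- *Steroid response at 3 to 5 days (6.5.2.2.2).* This implies at least one re-test but no continuing schedule.
- *Synopsis DLT clock.* Bilirubin above 3.0 and up to 5.0 x ULN must fall to Grade 2 within 7 days and Grade 1 within 14 to avoid being a DLT. Applying the clock needs bilirubin re-tests, but it covers Part A Cycle 1 only, and Section 4.2.4 does not repeat it.

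None of these sets a liver-test frequency that continues until bilirubin recovers.

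**The case against.** The strongest reply is that this is an editorial slip with little practical effect. The line is a floor inside general guidelines, allows more testing by judgment and tells nobody to stop. Both drugs are already off, so no dosing decision depends on it. An oncologist whose patient has bilirubin above 3 x ULN will keep testing. All of that is fair and limits the size of the point, but it does not make the end-point right. The protocol chose to set a numerical minimum for this event, and that minimum can expire while the event persists.

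Two ambiguities deserve disclosure.

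- If transaminases never rose, a clause about their return could be read as inapplicable, not as already satisfied. The firmest case is therefore bilirubin that lags behind recovered transaminases.
- The layout leaves it unclear whether the monitoring bullet covers all of Grade 3 or only bilirubin above 5 x ULN. On the narrower reading the end-point is still transaminases, and Grade 3 bilirubin at or below 5 x ULN has no stated minimum at all.

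It is also true that the 2.0 ratio compares grade limits. It does not measure missed tests, delay or harm.

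**Conclusion.** The concern holds. Under either reading of the layout, the twice-weekly minimum for Grade 3-4 bilirubin ends on the wrong analyte and can lapse while bilirubin is still Grade 3-4.

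The number of patients affected is probably small and cannot be estimated. The documents give no rate of Grade 3-4 bilirubin, nor of bilirubin that rises alone or recovers late. The conclusion rests on the wording and on the grade limits in the synopsis, with no incidence assumed. The consequence is confined to safety follow-up. The correction should be made because it is specific, protects patients and is cheap.

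**What to change.** In Section 6.5.2.2.2, change the end of the Grade 3 monitoring line to: *until total bilirubin (and transaminases, if elevated) have returned to Grade 1 or baseline*. Grade 4 then inherits the corrected rule.

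Keep the baseline alternative. Section 5.1 exempts patients with Gilbert's syndrome from the 1.5 x ULN bilirubin limit, "who may enroll if the conjugated bilirubin is within normal limits", so some may never return to Grade 1. While editing, set the bullet so that it plainly applies to all Grade 3 and 4 elevations.

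The cost is one phrase in a protocol amendment, with the usual sponsor and IRB/IEC approvals where required, plus a few more local chemistry draws in the few patients affected. With approximately 29 institutions involved, including it in the next planned amendment would be proportionate.

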6.5.2.3 Pneumonitis

Management guidelines for patients experiencing pneumonitis, are as follows:

- Grade 1 pneumonitis
 - No specific therapy required; close monitoring of lung function and imaging
- Grade 2 pneumonitis
 - Hold pembrolizumab and margetuximab. Begin corticosteroids: 1 to 2 mg/kg of oral prednisone or equivalent, per day divided twice daily
 - Taper over 4 weeks as clinically indicated
 - Resume pembrolizumab and margetuximab administration at next scheduled dose if pneumonitis resolves to \leq Grade 1 within 3 days with or without treatment.
 - Permanently discontinue pembrolizumab and margetuximab for recurrent Grade 2 pneumonitis.
- Grade 3 and 4 pneumonitis
 - Permanently discontinue pembrolizumab and margetuximab.
 - Hospitalize
 - Initiation of maximal supportive care including IV corticosteroids, suggest methylprednisolone at 2-4 mg/kg/day divided twice daily. Higher doses may be used in consultation with the Sponsor's medical monitor
 - If no response to corticosteroid therapy is observed within 3-5 days, consider adding immune suppression therapy (i.e., infliximab, etc.)

6.5.2.4 Dermatologic Toxicity

Management guidelines for patients experiencing dermatologic toxicity are as follows:

- Grade 1 or 2 skin reactions
 - Symptomatic treatment with low-dose topical corticosteroids (betamethasone 0.1% or hydrocortisone 1%) or antihistamines (diphenhydramine).
 - Persistent (7-14 days) Grade 1 or 2 rash should be managed with higher dose topical corticosteroids and/or oral prednisone (1-2 mg/kg/day) if there is not improvement with initial topical therapies or the rash is associated with other dermal toxicities such as pruritus.
- Grade 3 skin reactions
 - Hold pembrolizumab and margetuximab. Initiate oral corticosteroids (oral prednisone 1-2 mg/kg/day)
 - Pembrolizumab and margetuximab combination administration may be restarted at the next scheduled dosing if symptoms resolve to \leq Grade 2 within 14 days.
 - Grade 3 skin toxicity that does not resolve to \leq Grade 2 within 14 days of initiation of oral corticosteroids requires permanent discontinuation of study drugs.
- Grade 4 skin reactions
 - Discontinue pembrolizumab and margetuximab.
 - Initiate oral corticosteroids (oral prednisone 1-2 mg/kg/day)
 - Consideration should be given to start IV corticosteroids (methylprednisolone 1-2 mg/kg/day) for Grade 4 dermatologic toxicities with tapering on resolution to $<$ Grade 2 over 30 days.

